#### **14.1 Sample Size Determination**

This is a cross-over trial in which patients will be randomized to two different sequences of treatment.

The primary outcome measure will be the change in the weekly frequency of bowel movements between baseline and Week 2 of treatment (ie. Days 8 to 14, and Days 36 to 42). Efficacy will be assessed as the difference vs. baseline as well as the difference between the two treatments.

Given that this is a cross-over study, patient will serve as their own control and the statistical analysis will be based on matched comparisons. Depending on the distribution of the difference between the two treatments the parametric Paired Student's t-test, or non – parametric Wilcoxon's sign rank test will be used. The current sample size computation will be based on the parametric test, since this is more conservative and hence demanding of a higher sample size.

The following assumptions have been employed:

- i. The mean change in the lesser efficacious treatment will be 4 bowel movements per week.
- ii. The SD for the change in bowel movements per week will be 2.0 based on extrapolation of results from the literature (32).
- iii. The correlation of the changes between the two treatments will be 0.80 given that there is a strong patient effect on bowel movements. Hence the SD of the difference between treatment groups is 1.265 assuming an SD of 2.00 for each treatment group.
- iv. The significance level will be 0.05.
- v. The power of the study will be 80%.
- vi. The effect size to be detected will be between 10% and 25%.
- vii. Adjustment of 20% has been considered to compensate for attrition.

The following table describes the sample size requirements (number of patients) for the study by different effect size.

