Administration	
In each of the study periods, patients will be instructed to take two doses of ECC capsules daily (BID regimen), in the morning, at least 30 minutes before breakfast and before evening meal, for 14 days.
 
Patients randomized to Treatment A (Low dose, 1.7 g daily) will take 2 x 425 mg ECC capsules + 3 x placebo capsules in the morning and repeat in the evening.
 
Patients randomized to Treatment B (High dose, 4.25 g daily) will take 5 x 425 mg ECC capsules in the morning and repeat in the evening.
 
Capsules should be taken with water at ambient temperature. The capsules should be swallowed whole and not be chewed or crushed.

Dose Justification	Currently, at least 4 g daily is the dose recommended for regular, non-enteric coated cholestyramine. ECC may be as or more effective at a lower dose, i.e. 1.7 g daily.
Sample Size Justification	Using an alpha of 0.05 and beta of 0.2, a paired t-test, and assuming a standard deviation of 1.265 and a 20% attrition rate; 18 patients are required to show a minimal 25% difference between the two treatments in the reduction of the weekly number of bowel movements after 14 days of treatment (measured during the second week of treatment). Moreover, with 18 patients, we will have more than 80% power to detect a minimal reduction of 4 weekly bowel movements after 14 days of treatment with either 1.7 or 4.25 g of ECC per day (pooled data; assuming SD of 2).
Study Duration	12 - 16 months

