## **7. STUDY DESIGN**

### **7.1 Endpoints**

#### **7.1.1 Primary Endpoint**

The primary endpoint will be the change in the weekly frequency of bowel movements, measured between baseline and the second week of treatment (ie. Days 8 to 14 and Days 36 to 42). Efficacy will be assessed as the overall difference vs baseline as well as the difference between the two treatment doses.

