#### **7.1.2 Justification for the Primary Endpoint**

Several efficacy endpoints have been used in the study of the use of cholestyramine or other bile acids sequestrants in the management of bile acid diarrhea (BAD). These included fecal weight, fecal volume, weekly frequency of bowel movement (typically called 'number of stools' in the literature), mean stool type according to the Bristol Stool Form Scale (BSFS), loperamide use, etc. In a clinical trial in primary and secondary BAD, Walters *et al.* used an innovative

index taking into consideration the weekly stool frequency, the mean BSFS, as well as loperamide use (29). This index was: (weekly stool frequency X mean BSFS) + loperamide use. This index, while non-validated *per se*, was justified by the variable nature of BAD symptoms. All components of this index were influenced by the study treatment, obeticholic acid, in BAD patients.

Weekly stools (bowel movement [BM] frequency) is an objective endpoint that can be easily measured by patients, using a diary. BSFS can be more difficult to assess by study subjects, since it implies a visual evaluation of the stools and is consequently more subjective. Fecal weight and volume require regular stool collection, which is cumbersome.

In light of these considerations, the weekly number of bowel movements is proposed as the study primary efficacy endpoint. This endpoint is clinically relevant to the symptom of diarrhea, and an increased frequency translates to a decreased water reabsorption as well as an accelerated GI transit, both important pathogenic components of SBS. The data obtained from Walters and other authors show that bowel movement frequency (stool frequency) is a sensitive index for pharmacological intervention in SBS. While significant variability can be observed with this parameter, weekly bowel movement frequency can be greatly reduced by antidiarrheal drugs and bile acids modulating agents (e.g. obeticholic acid). Moreover, the second week of treatment with ECC will be used for this purpose, in order to reach an expected maximum and stable effect at each dose of the drug studied.

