## 12. EFFICACY ASSESSMENTS

### 12.1 Weekly Number of Bowel Movements

The total number of bowel movements (defecations) occurring during the second week of ECC treatment (Days 8 to 14) compared those occurring during screening in the week prior to randomization, will be used to assess the primary endpoint. Use of loperamide will also be recorded. Bowel movements will be recorded by the patients on a daily basis, as follows:

- each day of the last 14 days of the screening period, prior to randomization, to establish the first baseline and confirm subject eligibility
- each day of the first 14-day treatment period
- each day of the 14-day washout period
- each day of the second 14-day treatment period

[figure not shown]
In summary, this implies that occurrences of bowel movements will be recorded daily by the patient, in the diary, from Day -14 (screening) up to Day 42, i.e. the last dosing day of the study.

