## **14. STATISTICAL ANALYSIS**

A statistical analysis plan (SAP) will provide details of the methods of analysis to address all study objectives. The SAP may be amended during the course of the study but will be finalized before the database hard-lock for any analysis.

Data summaries by treatment group will be presented. For continuous variables, data will be summarized with the number of patients, mean, standard deviation, median, and minimum and maximum values by treatment group. For categorical variables, data will be tabulated in frequency tables to display the number and proportion of patients for each category by treatment group. Baseline assessments for each outcome variable will be defined as the last measurement obtained before the first dose of study drug.

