## 14.6 Efficacy Analysis

### 14.6.1 Analysis of Primary Endpoint

For the primary objective of the study, descriptive statistics will be produced for the change in weekly frequency of bowel movements between baseline and the second week of treatment. A sequential analysis approach will be used where:

- a. First, the efficacy of the High ECC dose (4.25 g daily) will be tested using a paired Student's t-test and a null hypothesis of 0. If this comparison shows a statistically significant improvement, then the efficacy of the Low ECC dose will be tested.
- b. To assess the efficacy of Low ECC dose (1.7 g daily) a paired Student's t-test and a null hypothesis of 0 will be used, similarly to above. If this comparison shows a statistically significant improvement, then the two doses will be compared.
- c. To compare the efficacy of the two doses, the absolute change in weekly frequency of bowel movements will be compared using a paired Student's t-test and a null hypothesis of 0 ( $\delta_{\text{High}} - \delta_{\text{Low}} = 0$ ).
- d. Given the sequential design of the analysis correction for multiplicity will not be required.

If the change in weekly frequency of bowel movements between baseline and the second week of treatment does not follow the normal distribution the non-parametric Wilcoxon signed rank test will be used.

The primary analysis will be conducted on the ITT population. The PP population will be used in a secondary analysis.

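### The 0.80 correlation behind the power of the dose comparison is justified by a patient effect that cancels when both changes are taken from the same baseline

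*Combined protocol and SAP*

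**What the plan says.** Section 14.1 assumes a mean change of 4 bowel movements per week on the less effective dose, an SD of 2.0 for each change (citing reference 32), 80% power and a 0.05 significance level. Item iii then states: "The correlation of the changes between the two treatments will be 0.80 given that there is a strong patient effect on bowel movements". From this it derives an SD of 1.265 for the difference between doses. Reference 32 is attached to the SD of 2.0 only; item iii has no source.

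Table 3 gives the sample size for differences of 0.40 to 1.00, all at that one SD. The last row (1.00, i.e. 25% of 4) gives 15, and 18 is recommended. The Synopsis puts it as "assuming a standard deviation of 1.265 and a 20% attrition rate; 18 patients are required". Section 14.1 also says that sizing on the t-test rather than the signed-rank test is the cautious choice because it demands more patients.

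On the baseline, Section 12.1 says that second-week counts "compared those occurring during screening in the week prior to randomization, will be used to assess the primary endpoint", and Section 14 adds: "Baseline assessments for each outcome variable will be defined as the last measurement obtained before the first dose of study drug".

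On the role of the comparison, Section 7.1.1 says: "Efficacy will be assessed as the overall difference vs baseline as well as the difference between the two treatment doses". In Section 14.6.1 it is the third step of the sequence, reached after the low dose is tested: "If this comparison shows a statistically significant improvement, then the two doses will be compared".

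**The concern.** The reason given for 0.80 concerns bowel movement counts, but the figure is used for changes from baseline. A patient who habitually has many bowel movements has many in the baseline week and in both treatment weeks. That makes the weekly counts correlate strongly. In a change from baseline the habitual level is subtracted, so it cannot by itself make the two changes correlate.

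Selecting the most effective dose is part of the primary objective (Section 6.1), and the 80% power claimed for that comparison depends on 1.265 and hence on 0.80. Section 7.1.2 itself concedes: "While significant variability can be observed with this parameter". If the true correlation is lower, a non-significant third step may only reflect low precision and could be misread as equal efficacy of the doses. The plan does not warn of this.

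**Working it through.** **1. Reproducing the plan.** With SD 2.0 per change and correlation r, the SD of the paired difference is √(2 × 4 × (1 − r)). At r = 0.80 this is √1.6 = 1.265. Exact noncentral-t power for a two-sided 0.05 paired t-test reproduces all 16 rows of Table 3 as evaluable patients; a difference of 1.00 needs 15 (power 81.2%). The plan does not state sidedness, but a one-sided test would give 12 in that row. The arithmetic is sound given its inputs.

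**2. What a patient level contributes.** Write each weekly count as patient level + treatment effect + weekly error, with error variance v₀ at baseline and v₁ in each treatment week.

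- Change = treatment effect + treatment-week error − baseline error; the level is gone.
- Variance of each change = v₀ + v₁.
- Covariance of the two changes = v₀, from the shared baseline error.
- Correlation of changes = v₀ / (v₀ + v₁), whatever the size of the patient level.

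Illustration (all inputs assumed): v₀ = v₁ = 2, no variation in response, patient-level SD 5. The two treatment-week counts correlate 25/(25 + 2) = 0.93. Each change has SD √4 = 2.0, as in the plan. The changes correlate 2/4 = 0.50. Simulation of a million patients with level SD 0, 2 and 10 gave count correlations of 0.00, 0.67 and 0.98, and a change correlation of 0.50 each time.

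**3. What could give 0.80** (assumed inputs, each with SD per change of 2.0 or very nearly so):

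- A patient-specific response shared by both doses with variance 2.4, and weekly error variance 0.8: (2.4 + 0.8)/4 = 0.80.
- A noisier baseline week, v₀ = 3.2 and v₁ = 0.8: 3.2/4 = 0.80.
- A common proportional reduction of 4/28, level SD 10.8, error variance 0.8: response variance (10.8/7)² = 2.38, so r = (2.38 + 0.8)/3.98 = 0.80.

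Section 14.1 argues none of these.

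**4. The quantity that needs support.** With a shared baseline the paired difference reduces to the second-week count on the high dose minus that on the low dose. With equal independent errors, an SD of 1.265 means 1.265/√2 = 0.89 bowel movements per week per period, in patients who enter with at least about 3 × 7 = 21 per week (inclusion criterion 10).

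**5. Power for a difference of 1.0**, SD 2.0 per change, two-sided 0.05:

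| Correlation | SD of difference | 14 evaluable | 15 evaluable | 18 evaluable | Evaluable n for 80% |
|---|---|---|---|---|---|
| 0.80 | 1.265 | 78% | 81% | 88% | 15 |
| 0.75 | 1.414 | 69% | 72% | 81% | 18 |
| 0.70 | 1.549 | 61% | 64% | 73% | 21 |
| 0.60 | 1.789 | 49% | 52% | 61% | 28 |
| 0.50 | 2.000 | 41% | 44% | 52% | 34 |

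The range 0.50–0.75 is an assumption; the true value is unknown. The largest SD of the difference that still gives 80% power is 1.234, 1.285 and 1.427 at 14, 15 and 18 patients, i.e. correlations of 0.81, 0.79 and 0.745.

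**6. Table 3 read differently.** Power depends only on difference/SD. The rows for 0.80, 0.72 and 0.64 (n = 22, 27, 33) are therefore equivalent to a difference of 1.0 with SDs of 1.581, 1.757 and 1.976, i.e. correlations of 0.69, 0.61 and 0.51. The plan does not present them this way.

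**7. Two smaller points.**

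- *Attrition.* 18 = 15 × 1.2. To keep 15 after a 20% loss needs 15/0.8 = 18.75, so 19. Conversely 18 × 0.8 = 14.4, about 14 patients, and 78.1% power even at 0.80.
- *Choice of test.* Under the normal model used for sizing, simulated signed-rank power (exact critical values) is 79.0% at 15 and 80.8% at 16, against 81.2% for the t-test at 15. The t-test is the less demanding of the two.

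**The case against.** The strongest reply is that a patient effect need not mean a stable level. It can also mean that patients differ in how far they respond, and that would make the changes correlate. The protocol's background fits this: Section 5.4 reports 10 of 12 patients with shorter resections responding and none of eight with longer ones, and Section 5.5 quotes 75–88% effectiveness for conventional resins. With all-or-none response, the same responders and the same response at both doses, mean change 4, SD 2.0 and equal weekly errors (all assumed), 87% responders gives a correlation of 0.80. So 0.80 is plausible and 0.50 should not be taken as the best guess. But Section 14.1 does not make this argument, and it is sensitive: 85% responders gives 0.85 and 88% gives 0.77.

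Secondly, Section 12.1 calls the screening diary the first baseline, which may hint at a second. None is defined for the primary endpoint, and a separate baseline for each period would lower the additive-model correlation to 0, not raise it.

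Thirdly, the assumptions are declared, Section 8.6 permits replacement of lost patients, and with 18 evaluable patients power stays at or above 80% down to about 0.745. All true, which limits the consequence. But replacement is optional, and neither the Synopsis nor Section 14.1 shows how far the power depends on this input.

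Finally, with heavy-tailed data the t-test can need more patients than the signed-rank test. That is correct, but the sizing was done under normality, where it does not.

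**Conclusion.** The concern holds. The stated reason does not support a 0.80 correlation between changes, no source is given, and the 80% power for the dose comparison rests on it. The finding is that 0.80 is unsupported; it is not shown to be false.

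With 15 evaluable patients, a fall from 0.80 to 0.75 takes power from 81% to 72%. At 0.50, the value under a purely additive patient level with equal weekly errors, power is 44% with 15 and 52% with 18, and 34 evaluable patients would be needed. Separately, and without questioning 0.80, the planned 18 patients less 20% give 78% rather than 80% unless losses are replaced. The attrition and choice-of-test points are each worth about one patient.

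The problem is confined to the dose comparison. Power to detect a reduction of 4 from baseline with SD 2 does not use the correlation and exceeds 99% even with 14 patients. The validity of all three tests is also unaffected.

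**What to change.** Keep 18 patients and make the power statement conditional.

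- **Section 14.1 and Synopsis.** State: *Assuming an SD of the within-patient difference of 1.265 (SD 2.0 per change, correlation 0.80), power for a difference of 1.0 bowel movement per week between doses is about 81% with 15 evaluable patients, 78% with 14 and 88% with 18. Power is at least 80% for an SD of the difference up to 1.23, 1.28 and 1.42 with 14, 15 and 18 evaluable patients.*
- **Item iii.** Replace the patient-effect reason with a source for the correlation or, more directly, for the SD of the within-patient difference. If there is none, add the power table for correlations 0.50 to 0.80.
- **Choice of test.** Delete the statement that sizing on the t-test is the more demanding option.
- **Section 14.6.1 or the SAP.** Report the between-dose difference with its 95% confidence interval, so that a non-significant third step is not read as equal efficacy.

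The cost is a few sentences, at most one small table and one reporting line, with no extra patients, visits or data. The stated power becomes conditional and slightly less favourable.

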**Table 3 - Sample Size Requirements by Size Effect**

ECC - A	ECC - B	Percent Difference (%)	Absolute Difference	Sample Size
4.00	4.40	10	0.40	81
4.00	4.44	11	0.44	67
4.00	4.48	12	0.48	57
4.00	4.52	13	0.52	49
4.00	4.56	14	0.56	43
4.00	4.60	15	0.60	37
4.00	4.64	16	0.64	33
4.00	4.68	17	0.68	30
4.00	4.72	18	0.72	27
4.00	4.76	19	0.76	24
4.00	4.80	20	0.80	22
4.00	4.84	21	0.84	20
4.00	4.88	22	0.88	19
4.00	4.92	23	0.92	17
4.00	4.96	24	0.96	16
4.00	5.00	25	1.00	15

Values are the mean change in bowel movement frequency (number of bowel movements per week) between baseline and Week 2. Higher values indicate a greater reduction in stool frequency.

Based on the above assumptions and assuming a 25% difference between treatments, a total sample size of 18 patients is recommended. It is expected that about 6 patients will be randomized at each of the 3 participating clinical sites.

With 18 patients, we will have more than 80% power to detect a minimal reduction in the weekly number of bowel movements by 4.

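### The 20% attrition allowance in Section 14.1 gives 18 where 19 is needed; the effect on power is 1 to 2 points, and the remark that the t-test is the more demanding test should go.

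*Combined protocol and SAP*

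**What the plan says.** Section 14.1 sizes the trial on the comparison of the two doses with a paired t-test. Its inputs are:

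- "The significance level will be 0.05", with no statement of one or two sides.
- "The power of the study will be 80" percent.
- "The mean change in the lesser efficacious treatment will be 4 bowel movements per week".
- "The SD for the change in bowel movements per week will be 2.0", with a correlation of 0.80 between the two changes, giving an SD of 1.265 for the paired difference.
- "Adjustment of 20% has been considered to compensate for attrition", with no formula.

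Table 3 lists 15 patients for a 25% difference. The text below it says that, "assuming a 25% difference between treatments, a total sample size of 18 patients is recommended". The synopsis repeats the claim as "assuming a standard deviation of 1.265 and a 20% attrition rate; 18 patients are required to show a minimal 25% difference".

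Section 14.1 also explains why the t-test, and not the Wilcoxon signed rank test, was used for sizing: "since this is more conservative and hence demanding of a higher sample size". Section 14.6.1 names the signed rank test as the fallback if the change is not normally distributed. Section 8.6 allows patients who withdraw or are lost to be replaced so that the evaluable number from the sample size calculation is reached.

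**The concern.** An attrition rate is a fraction of those randomised, so the evaluable number has to be divided by one minus that rate. Multiplying by one plus the rate gives too few patients. Going from 15 to 18 looks like the multiplication. If so, the three figures that the synopsis puts together (80% power, 20% attrition, 18 patients) cannot all hold for the dose comparison, which is the comparison that fixed the sample size.

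The remark on the t-test is a separate matter. It suggests that the calculation carries a margin should the analysis move to the signed rank test. If the remark is wrong for the model used, that margin is not shown.

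**Working it through.** **Inputs.** From Section 14.1: alpha 0.05, power 80%, SD of change 2.0 per dose, correlation 0.80, smaller mean change 4 per week. From Table 3 and the text below it: difference 25% of 4 = 1.0 per week. Attrition 20%: Section 14.1 and the synopsis. Two-sided testing is an assumption, checked in step 2. A lost patient is taken to contribute no paired difference.

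**1. SD of the paired difference.** sqrt(2 x 2.0² x (1 − 0.80)) = sqrt(1.6) = 1.265, as the plan states.

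**2. Table 3.** Power of the paired t-test with n patients comes from the noncentral t distribution with n − 1 degrees of freedom and noncentrality (1.0/1.265) x sqrt(n). The smallest n that reaches 80% with two-sided alpha 0.05 is 15. The same method, with the difference changed row by row, reproduces all 16 rows of Table 3 exactly. At 25%, a one-sided test gives 12 and a normal approximation gives 13, so neither fits. Table 3 is therefore correct for a two-sided paired t-test and holds no attrition allowance.

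**3. From 15 to 18.** 15 x 1.2 = 18, the plan's figure. 15/(1 − 0.20) = 18.75, so 19. Conversely, 20% of 18 lost leaves 18 x 0.8 = 14.4, below the 15 required. The loss that 18 can bear is (18 − 15)/18 = 16.7%.

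**4. Power for the dose comparison (difference 1.0, SD 1.265).**

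| Evaluable patients | Paired t-test power |
|---|---|
| 14 | 78.1% |
| 15 | 81.2% |
| 18 (no loss) | 88.5% |

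If the number of completers is Binomial(18, 0.8), average power is 78.8% and the chance of fewer than 15 completers is 50%. With 19 randomised, average power is 81.2%.

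**5. The other power claim.** For a reduction of 4 from baseline with SD 2, power exceeds 99.9% even with 14 patients.

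**6. t-test against signed rank test.** These are simulations with 40,000 runs per case, exact critical values, and the same mean and SD of the difference as above. With normal differences, signed rank power is 76.4% at 14, 78.9% at 15 and 80.9% at 16. It therefore needs 16 where the t-test needs 15. This agrees with the large-sample efficiency of 3/π = 0.955, since 15/0.955 = 15.7. With heavy-tailed differences (t with 3 degrees of freedom, same SD) and 14 patients, the order reverses: signed rank 89.9%, t-test 84.8%. With uniform differences and 14 patients it is 70.2% against 77.5%.

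**The case against.** There is a fair case for leaving the number alone, and most of it stands.

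- **Replacement.** Section 8.6 provides for exactly this shortfall, and 15 evaluable patients give 81.2%. This stands as mitigation. Replacement is optional, however, and the sample size text does not rely on it, so it does not make the stated combination correct.
- **Size.** The gap is one patient and 1 to 2 points of power, smaller than the uncertainty in an SD extrapolated from the literature and an assumed correlation of 0.80. This stands, and is why the point is minor.
- **Wording.** Section 14.1 speaks only of a 20% adjustment, and 15 plus 20% is literally 18. That reading is open there, but the synopsis speaks of an attrition rate, which calls for division.
- **Choice of test.** The plan turns to the signed rank test only when normality fails, and there it may be the more powerful test. This stands. It means that neither ordering can be claimed in general, including the one the plan asserts.

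A reader might infer that 18 patients cannot deliver the stated power, or that the trial needs to enrol more. The documents do not support that: with 15 or more evaluable patients the dose comparison keeps its 80%, and the claim about a reduction of 4 is met with room to spare. A reader might also think that the remark on the t-test helped to cause the shortfall. It did not, because the number was computed for the t-test and Table 3 is right for that test.

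**Conclusion.** The justification is wrong as written, to a minor degree. Under the plan's own inputs, 80% power with 20% attrition needs 19 randomised, not 18. With 18 randomised, a 20% loss and no replacement, power for the dose comparison is about 78–79%. This rests on two-sided testing (not stated, but the only version that fits Table 3), on lost patients contributing no paired difference, and on the 15 x 1.2 step, which is inferred. The finding that 14.4 expected completers fall short of 15 does not depend on that inference.

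The statement that the parametric test demands the larger sample is a second, independent error. It is false under the normal model behind Table 3, and elsewhere it is true or false according to the shape of the differences.

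**What to change.** In Section 14.1 and the synopsis, state that:

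- 18 randomised gives at least 80% paired t-test power for the dose comparison provided at least 15 are evaluable, that is, with a loss of up to 3 patients (16.7%);
- at 20% loss without replacement, that power is about 78–79%;
- Section 8.6 permits replacement to reach 15 evaluable patients but does not guarantee it.

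As a separate edit, delete the statement in Section 14.1 that the parametric test is the more conservative choice and requires the larger sample. Do not put signed rank power percentages in its place as general figures, since they depend on the distribution assumed.

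The cost is a text correction and a slightly less favourable power statement. No extra enrolment and no change to the analysis is needed.
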